A review of current literature found studies comparing SSD to other silver type dressings, SSD to Mepitel, and silver type dressings to topical antibiotic ointments. Search results failed to return articles on the soft cast technique for the treatment of burn wounds or the use or efficacy of Mepitel Ag. According to the literature, many silver containing products including SSD, Acticoat (silver rayon mesh), and Aquacel Ag (hydrofibre with silver ion) are indicated for partial to full thickness wounds, suggesting silver's ability to penetrate deeper burn injuries to promote wound healing.¹ Many studies found the silver type dressings to be associated with shorter healing time when compared to SSD and antibiotic impregnated gauze.

One important component of a burn dressing is “the creation of a moist wound-healing environment, the prevention of crust formation, and the physical protection of the wound against mechanical disturbances”.²⁸ In one review, antibiotic ointment impregnated gauze demonstrated adherence to the wound bed, causing damage to newly epithelialized cells during the dressing change.²⁸ In addition, Bacitracin, a component of TAO has been linked to promoting yeast colonization on healed wounds.⁷ Another study found yeast infections rates to be higher among children in the 1-16 year old age range, contributing this finding to “a higher sensitivity for Candida infections during childhood”.²⁰

Burn dressing changes have been reported as being some of the most traumatic and painful procedures for children.^{10, 23} In addition, daily dressing changes are rather time consuming and costly.²⁸ When determining acute burn wound care, it is important to utilize dressings that optimize wound healing while decreasing dressing frequency and subsequent patient pain. Mepitel, a grid like soft silicone coated nylon dressing that adheres only to intact skin, was found to demonstrate shorter wound healing time, less eschar formation, decreased pain, and lower cost when compared to SSD in one clinical trial.^{28,5} According to a study by Briggs et al, “silicone –based non-adherent dressings are especially beneficial in reducing pain during dressing changes in children.”³

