Patients to be included in this study will be all Children's Hospital Colorado burn patients between the ages of 31 days and 18 years with newly diagnosed partial to deep partial or full thickness hand or foot burns, including bilateral or unilateral injury. Each injured extremity will serve as a separate data point. Exclusions include age > 18 years at start of study, silver allergy, silicone allergy, electrical or chemical burn, past medical history of immunodeficiency disorders such as diabetes mellitus, AIDs, or HIV, pregnant women, prisoners children under the protection of the department of human services, and the decisionally challenged.

C. Study Design and Research Methods

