New burn clinic patients identified with a partial to deep partial or full thickness hand or foot burn will be randomized into either the Mepitel Ag group or the control group on their first clinic visit based on burn wound severity and age using RedCap. The randomization scheme in RedCap will be independently created by a statistician. Parental consent and or patient assent will be obtained prior to initial dressing. Burn severity will be clinically determined by one provider and one burn nurse during initial exam based on a 10 point burn severity classification scale in regards to the following parameters: 1) Superficial first degree- wound appears pink or red, involves epidermis only, no blisters present, dry; 2) Second degree, superficial partial thickness- burn involves epidermis + dermis, red or bright pink in color with blisters and or swelling, blanches, moist appearing; 3) Second degree, majority superficial partial thickness, minority superficial- burn involves majority ($\geq 66\%$) superficial partial thickness, epidermis + dermis, red or bright pink in color with blisters and or swelling, blanches, moist appearing, minority ($\sim 33\%$ or less) superficial first degree with areas of redness but no blistering; 4) Second degree, majority partial thickness, minority deep partial thickness- majority of burn ($\geq 66\%$) epidermis + dermis, red or bright pink in color, moist, less than half of burn ($\sim 33\%$ or less) is deep with pale pink-white areas, may or may not have a marbled or mosaic appearance; 5) Second degree, deep partial thickness- involves epidermis + dermis, pale pink to white in color, may have thin white moist eschar, may or may not have a marbled or mosaic type appearance, moist; 6) Second degree, majority deep partial thickness, minority superficial partial thickness- minority of burn ($\sim 33\%$ or less) involves epidermis + dermis, red or bright pink in color, moist, majority ($\geq 66\%$) of burn is deep with pale pink-white areas having a marbled or mosaic appearance, may or may not have thin white moist eschar, skin buds may or may not be present; 7) Second degree, deep partial thickness with areas of full thickness- majority of burn ($\geq 66\%$) involves epidermis + dermis, pale pink to white in color, may have thin white moist eschar, may or may not have a marbled or mosaic type appearance, moist, skin buds may or may not be present, minority of burn ($\sim 33\%$ or less) demonstrates thin to thick area of eschar white, brown or black in color, may need skin graft to heal; 8) Third degree full thickness with minority partial thickness- majority of burn ($\geq 66\%$) involves entire dermis + epidermis, thin to thick eschar that is white, brown or black in color, dry appearing, minority of burn ($\sim 33\%$ or less) is pink or red and moist, with blisters and or swelling, blanches; 9) Third degree full thickness- involves entire dermis + epidermis, thin to thick eschar that is white,

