
brown or black in color, dry appearing; 10) Fourth degree- third degree + muscle and or bone involvement. The provider and burn nurse will each give the patient a number and the severity will be determined based on the average of the 2 numbers. Any patient given a number 2, 3 or 4, will be placed into the "partial thickness" category, any patient given a 5, 6, or 7 will be placed into the "deep partial thickness" category, and lastly, any patient given an 8 or 9 will be placed into the "full thickness" category for burn severity.

Patients will be randomized into one of two groups, Mepitel Ag or standard TAO, using RedCap and based on a random clinical trial excel spread sheet balanced by burn severity. A statistician will provide a randomization scheme for investigators to follow. Photographs will be taken prior to dressing application at the initial visit and each subsequent visit. ~~Patient wounds will be dressed in either Mepitel Ag, kling or kerlex, cast padding, gypsoma plaster, soft cast material and coban for up to 21 days or until complete re-epithelialization of the wound occurs or unless surgery is indicated; the control, standard dressing of Triple Antibiotic Ointment impregnated adaptic gauze, kling or kerlex, cast padding, gypsoma plaster, soft cast material and coban for 10-14 days, or Nystatin impregnated adaptic, kling or kerlex, cast padding, gypsoma plaster, soft cast material and coban for 8-21 days or until complete re-epithelialization of the wound occurs or surgery is indicated. The SCT is applied by Occupational and Physical trained in casting and positioning. The soft cast provides optimal positioning while eliminating friction on the burn area. Dressing changes will occur every 3-10 days and will be determined by the provider, based on burn wound severity. Upon each return clinic visit, the patient will have their wound severity assessed by the following scoring system: 1=0% healed, 2=20% healed; 3=40% healed; 4=60% healed; 5=80% healed; 6=100% healed. This will be established by provider and burn nurse examination of the wound. This will be recorded in RedCap:_____~~

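### Randomisation is described once as based on severity and age and once as balanced by severity, with no age bands, and no analysis names either factor as a covariate

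*Combined protocol and SAP*

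**What the plan says.** Section IV.C (Study Design and Research Methods) describes the allocation twice.

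- The first statement randomises new patients "on their first clinic visit based on burn wound severity and age using RedCap", and adds: "The randomization scheme in RedCap will be independently created by a statistician".
- The second statement, after the severity scale, again names RedCap but describes the allocation as "based on a random clinical trial excel spread sheet balanced by burn severity". Age is not mentioned. It continues: "A statistician will provide a randomization scheme for investigators to follow".

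Both statements are current text; the struck-through wording in that section begins after them. Severity is grouped into three categories by score (2 to 4, 5 to 7, 8 or 9). No age bands, block size or allocation method appear anywhere.

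Section IV.B admits children "between the ages of 31 days and 18 years". Section III reports that one study found "yeast infections rates to be higher among children in the 1-16 year old age range".

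Section IV.F plans Kaplan-Meier curves, a log-rank test and a Cox model for healing time, logistic regression for debridement and yeast, and two-sample t-tests and chi-squared tests for pain and pain medication. It names no covariate in any of these. Section IV.E lists uneven groups as a possible limitation and gives no remedy.

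**The concern.** The person who builds the allocation table has two descriptions of the same step and no rule for choosing between them. A table stratified by severity can be set up from the second description. A table stratified by severity and age needs a decision on age bands that the protocol does not record. It is therefore quite possible that age drops out at the building stage while the protocol still says that it was used.

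If so, age would be left to simple chance across a very wide range, in a trial of modest size. The analysis plan would not recover the lost precision, because no model is said to include age. The same gap affects severity, which is named in both descriptions. Balancing on a prognostic factor and then leaving it out of the analysis generally gives standard errors that are too large for the design. The outcomes most exposed are the pain comparisons, because the tests named there cannot carry a covariate at all.

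**Working it through.** The plan gives no figure on this point to reproduce. The check has three parts: the text, the analysis plan, and the size of a chance imbalance.

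**1. The two statements.** The first names severity and age; the second names severity. The second does not say severity alone, so a severity-and-age table would satisfy both, while a severity-only table would satisfy only the second. The text does not exclude either table.

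**2. Use of the factors in the analysis (section IV.F).**
- Healing time: log-rank and Cox; no stratum or covariate named.
- Debridement and yeast: logistic regression; no covariate named.
- Pain and pain medication: two-sample t-tests and chi-squared tests, which use neither factor.
- Baseline characteristics are compared between arms, but no adjustment follows from the result.

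**3. Chance imbalance if age is not a stratum.** From section IV.F: 50 per group, 100 burns. Assumptions: the age split, the share of children with two burned limbs, and the yeast rates.

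*Two age bands, normal approximation.* The 95% range of the between-arm difference in the younger share is ±1.96 × √(4p(1−p)/N).
- p = 0.5, N = 100 children: 1.96 × √(1/100) = 0.196, about ±20 points.
- Section IV.B counts each limb as a data point, so 100 burns may mean fewer children. If 30% have two burned limbs, N = 100/1.3 ≈ 77, and 1.96 × √(1/77) = 0.223, about ±22 points.

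*Two age bands, exact (hypergeometric, 50 per arm, one burn per child).*

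| Share in younger band (assumed) | Chance of a difference of 10 points or more | Chance of 20 points or more |
|---|---|---|
| 30% | 27.5% | 4.9% |
| 50% | 31.7% | 7.1% |

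*Age as a continuous variable.* The standard error of the standardised mean difference is √(2/50) = 0.20. The chance of a difference of at least 0.25 SD is 2(1 − Φ(1.25)) = 21%; of at least 0.3 SD, 13%; of at least 0.4 SD, 5%.

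*What that does to an outcome.* The shift equals the gap in outcome rate between bands times the imbalance. If yeast rates differ by an assumed 10 to 20 points, a 20-point imbalance shifts the comparison by 0.10 × 0.20 = 2 points to 0.20 × 0.20 = 4 points. For scale, at an assumed yeast rate of 10% the standard error of the arm difference is √(2 × 0.10 × 0.90/50) = 6 points; at 20% it is √(2 × 0.20 × 0.80/50) = 8 points.

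*Cells if age is added.* 3 severity categories × 2 age bands = 6 cells, averaging 100/6 ≈ 17 children, or 77/6 ≈ 13.

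**The case against.** The strongest reply is that this is an incomplete restatement and not a conflict. A scheme using both factors obeys both sentences, and both leave the building of the scheme to a statistician, who can set age bands at that stage. Block size is also missing, for severity as much as for age, so missing detail does not show that age was dropped. All of that stands. A reader might infer that the two statements cannot both be followed, or that age balancing will certainly not happen; the text supports neither.

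It is also fair to say that randomisation balances age in expectation, that the planned tests' error rates already allow for chance imbalance, and that the plan compares demographics between arms, so an imbalance would be seen. A reader might infer bias from the word unbalanced; the risk is chance imbalance and lost precision.

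The link from age to outcome is thin. The documents nowhere say that FLACC or parent-rated pain varies with age. The yeast statement concerns ages 1 to 16, which covers most of the eligible range and so says little about a gradient within the trial. It does not show that an excess of infants and toddlers would raise yeast rates, and it does not support a cut at 2 years, which would pool children outside that band with children inside it.

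Finally, logistic and Cox models can carry covariates; the plan leaves them unnamed and does not rule them out. That is true, but it does not help the pain tests, and a covariate chosen after the data are seen is worth less than one named now.

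What survives is narrow: one statement omits a factor that the other names, the bands needed to use that factor are missing, and the analysis plan names neither factor.

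**Conclusion.** The point holds as a gap in specification with a modest statistical cost. The allocation could be built without age, and age would then not be balanced by design. The 95% range of the resulting chance imbalance is about ±20 percentage points for a 50:50 age split with 100 children, or ±22 with 77. That figure describes imbalance in age, not an effect on any outcome. For yeast, even a 20-point imbalance (a 5% to 7% chance) shifts the comparison by 2 to 4 points under assumed rate gaps, which is less than one standard error. No corresponding figure can be given for pain, because the documents do not relate pain to age.

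The firmer part concerns the analysis: whichever scheme is built, the plan as written uses neither randomisation factor in any model, and the pain tests cannot use them. The age split, the share of children with two burned limbs, and the yeast rates are assumptions; the group size and eligibility range come from the protocol.

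**What to change.** Before allocation starts:

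1. Make the second randomisation statement in section IV.C match the first: stratified by burn severity (three categories) and age at randomisation (two pre-specified bands). The trial statistician should set and record the age cut. State the allocation method and how the spreadsheet relates to RedCap.
2. In section IV.F, include severity and age in the Cox and logistic models, and replace the pain t-tests with linear regression on treatment, severity and age. Use logistic regression in place of the chi-squared test for pain medication use.

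If six strata are thought too many, delete age from the first statement and keep it as a covariate in the analyses. That also resolves the discrepancy and recovers most of the precision.

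The cost is a few sentences and a rebuilt allocation table; both factors are known at the first visit. The downsides are small. Some full-thickness cells will be sparse, whatever the average of 13 to 17 children suggests. The yeast model may also have few events: at an assumed 10% to 20% rate, 100 burns give 10 to 20 events for four terms (treatment, two for severity, one for age), or 2.5 to 5 per term. A penalised logistic fit should be named as the fallback.

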A comparison of Mepitel Ag vs antibiotic ointment when used with a soft cast technique for the treatment of pediatric hand and foot burns, a prospective study

Protocol #: 15-1828

April 8, 2016

COMIRB Protocol

COLORADO MULTIPLE INSTITUTIONAL REVIEWBOARD
[name] [contact] [contact]

Protocol #: 15-1828

Project Title: A comparison of Mepitel Ag vs antibiotic ointment when used with a soft cast technique for the treatment of pediatric hand and foot burns, a prospective study

Principal Investigator: [name], MD

Version Date: 3/30/16

- I. **Hypotheses:** Mepitel Ag in combination with the soft cast technique improves wound healing in pediatric partial to deep partial thickness hand and foot burns by decreasing the length of healing time, decreasing the risk of yeast infection, and decreasing pain associated with multiple dressing changes.
- II. **Specific Aims:**
 - 1) To examine the efficacy of Mepitel Ag for use in pediatric partial to deep partial thickness hand and foot burns.
 - 2) To evaluate Mepitel Ag to triple antibiotic ointment when used in combination with a soft cast technique comparing healing time, yeast infection rates and pain levels at time of dressing change.

II. Background and Significance:

There is currently no gold standard dressing when it comes to treating hand or foot burns, specifically in the pediatric population. Our institution currently utilizes a soft cast technique (SCT) on all of our hand and foot burns. The SCT provides optimal positioning of the wounded hand or foot, allows for a moist wound environment, and offers protection of the injured extremity as the wound heals. Our current SCT uses triple antibiotic ointment (TAO) impregnated Adaptic gauze, kling or kerlex, cast padding, gypsoma plaster, soft cast material, and coban. This dressing is applied two to three times during the first 2 weeks post injury. To reduce the risk of the development of yeast overgrowth, the underlying dressing is changed to nystatin impregnated Adaptic gauze, kling or kerlex, cast padding, gypsoma plaster, soft cast material, and coban for the remainder of treatment time or until OR is indicated for surgical debridement and grafting of wounds..

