A review of the current literature demonstrates silver sulfadiazine (SSD) to be the most frequently used dressing for burn wound treatment in many clinics nationwide.²⁸ The use of SSD is associated with once to twice daily painful dressing changes and wound exposure that "may lead to disruption of newly formed epithelium, wound colonization, subsequent wound infection and deepening of the burn".^{23, 28} One major benefit of the SCT is the reduction in

required dressing changes, as the soft cast can stay in place for 7-10 days while maintaining optimal hand or foot positioning. This eliminates the need for frequent painful dressing changes.

Occasionally, We have observed yeast infections when patients require serial casting and all have been treated with antibiotics. Other complications we have experienced include: occasional drying out of the adaptic gauze leading to a painful dressing removal and interruption of the newly epithelialized wound bed.

Mepitel Ag, a new soft silicone dressing produced by Molnlycke Health Care, combines Safetac technology with a silver compound to provide a broad spectrum of antimicrobial coverage. The safetac technology “protects the wound and the skin. It prevents an outer dressing from sticking to the wound, therefore minimizes trauma and pain”.¹⁵ The highly pliable nature and antimicrobial properties of the dressing make it an ideal alternative to TAO and SSD for the treatment of pediatric partial to deep partial thickness hand and foot burns. The silver compound lasts up to 8 days, while minimizing damage to the new epithelium and creating a moist wound environment. As Mepitel Ag is a relatively new product, there are currently no studies analyzing its efficacy and effectiveness when compared to other burn treatment methods.

The aim of this study is to compare Mepitel Ag to triple antibiotic ointment impregnated Adaptic gauze when used with the soft cast technique to assess overall time to healing, yeast infection rate and parents perception of pain level at time of dressing change on a scale of 1-10. The hypothesis is that Mepitel Ag in combination with the soft cast technique improves wound healing in pediatric partial to deep partial thickness hand and foot burns by decreasing the length of healing time, decreasing the risk of yeast infection, and decreasing pain associated with dressing changes.

III. Preliminary Studies/Progress Report:

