A member of the nursing team will also complete a questionnaire at each follow up visit to indicate pain level with dressing change based on the FLACC scale, parents perceived level of pain during dressing change, parental reported pain level at home, use of home pain medications, type of home pain medication- narcotic vs non-narcotic, clinical assessment of yeast rash including odor, visible rash, use of fluconazole, ease of dressing application, and amount and type of product used in dressing change.

D. Description, Risks and Justification of Procedures and Data Collection Tools:

A photography release will be distributed and signed by parent at initial visit.

Anursing questionnaire will be completed by nursing staff at each follow up appointment.

Local wound care including cleansing, wound measurement and dressing change will be performed by burn team including nursing staff and occupational and physical therapists. Although punch biopsy with histological analysis is considered the 'gold standard' in assessing burn wound depth, it is invasive and time consuming.¹⁸ Clinical assessment remains the most frequent and rapid method.¹⁸ Due to the time sensitive nature of the proposed trial and in order to avoid delaying wound care and initial dressing application, a 10 point clinical assessment scale has been created, as listed above for use in determining initial burn wound severity. Patient wound depth will be clinically determined by the average of the scores from the provider and the burn nurse.

The wound will also be assessed by the provider and nurse on subsequent visits using the following scoring tool: 1=0% healed, 2=20% healed; 3=40% healed; 4=60% healed; 5=80% healed; 6=100% healed. This will be established by provider and burn nurse examination of the wound. This will be recorded in RedCap.

The overall risk for this study is minimal, with no foreseen adverse reactions. The risk of a silver allergy or adverse reaction to silicone is very rare.

E. Potential Scientific Problems:

Limitations to the proposed study design include varying diagnostic opinions between provider and burn nurse for the determination of superficial vs deep partial thickness burn wounds based on clinical assessment, provider or nurse bias based on dressing preference, and possible uneven trial groups.

F. Data Analysis Plan:

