Analysis Plan: Demographic and clinical characteristics will be summarized and compared between the two treatment groups using chi-squared and two-sample t-tests for categorical and continuous data, respectively. For analysis of the primary outcome, time to wound healing, we will use Kaplan-Meier curves, the log-rank test and a Cox proportional hazards model to determine the difference in days to re-epithelialization between the TAO and Mepitel Ag soft cast methods. Patients that require surgical intervention will be censored at the time of surgery. Logistic regression will be used to analyze the secondary outcomes, need for surgical debridement and occurrence of yeast infection. Pain level outcomes and pain medication use will be compared using two-sample t-tests and chi-squared tests. Cost effectiveness outcomes will also be analyzed.

1. Sample size: A statistical power analysis was performed to estimate power, based on results reported in A Soft casting Technique to Manage Pediatric Hand Burns: Less Pain, Greater Gain.²² Considering the simplest between group comparison and assuming a standard deviation of 0.3, alpha of 0.05 and 50 subjects per group there is over 90% power to detect a difference of 2 days between the treatment groups. Thus, we expect that our proposed sample size of 100 burns will be adequate for the main objective of this study.

G. Summarize Knowledge to be Gained:

To demonstrate that Mepitel Ag in combination with a soft cast technique improves wound healing in pediatric partial to deep partial thickness hand and foot burns by decreasing the length of healing time, decreasing the risk of yeast infection, and decreasing pain associated with dressing changes.

H. References:

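### Healing is seen only at provider-timed visits, yet the primary log-rank and Cox analysis ignores the interval censoring; if visit spacing differs by arm, the recorded effect shifts by about half that difference

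*Combined protocol and SAP*

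**What the plan says.** On timing, Section IV.C states: "Dressing changes will occur every 3-10 days and will be determined by the provider, based on burn wound severity". No table links severity to interval. The sentence sits in a block that the text extraction shows as struck through. If it really was deleted, no trial-specific schedule remains, but the Background still says that "the soft cast can stay in place for 7-10 days".

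On assessment, Section IV.D states: "The wound will also be assessed by the provider and nurse on subsequent visits using the following scoring tool". The tool runs in steps of 20%, up to 100% healed, and is recorded in RedCap. The wound is under a cast between visits.

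On analysis, Section IV.F states: "we will use Kaplan-Meier curves, the log-rank test and a Cox proportional hazards model to determine the difference in days to re-epithelialization". The only censoring rule is censoring at surgery.

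On allocation, Section IV.C makes the randomization "based on a random clinical trial excel spread sheet balanced by burn severity".

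On regimens, the Background says of the current TAO cast: "This dressing is applied two to three times during the first 2 weeks post injury". It is followed by nystatin dressings. Section IV.C (same struck-through block) gives the control arm "Nystatin impregnated adaptic, kling or kerlex, cast padding, gypsoma plaster, soft cast material and coban for 8-21 days". Of Mepitel Ag, the Background says: "The silver compound lasts up to 8 days". Section IV.E lists staff preference for a dressing as a possible source of bias.

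**The concern.** The trial will know only that a burn healed between two visits. Standard Kaplan-Meier, log-rank and Cox methods need a single date. The plan names none; the natural reading, which is an inference, is the date of the first visit scored 100%. That date is late by about half a visit interval on average.

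A delay common to both arms does no harm to the comparison. A delay that differs by arm is read as a treatment effect. Severity should not create such a difference, because allocation is balanced on it. The dressing might: the regimens differ, the provider sets the interval, no blinding is described, and clinic visits and soft casts are themselves listed as outcomes in Section IV.A. At stake is a distortion, in either direction, of a planned difference of only 2 days.

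**Working it through.** **The plan's own figure.** Section IV.F gives 50 per group, SD 0.3 and a difference of 2 days. The standardized difference is 2 / (0.3 × √(2/50)) = 2 / 0.06 = 33.3, so power is about 100%, which agrees with the stated figure of over 90%. The SD is a separate matter. Only the 2-day yardstick and the group size are used here.

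**Delay within an arm.** Take recorded healing as the first visit at or after true healing. If intervals have mean m and variance v and vary from visit to visit, the mean delay is about m/2 + v/(2m). With fixed intervals it is m/2. Simulation with assumed gamma healing (mean 10-14, SD 3-6 days) gave 1.5 days at 3-day visits, 3.5-3.6 at 7, 4.0-4.1 at 8 and 4.6-5.2 at 10.

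**Difference between arms.** The shift is the Mepitel Ag delay minus the TAO delay, about half the difference in mean interval. A positive value means TAO healing is recorded too early relative to Mepitel Ag. In simulation, 5 v 7 days gave 0.9-1.0 day and 5 v 9 days gave 2.0-2.1 days. Equal schedules gave about 0.

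**Intervals the documents allow.** Two to three TAO casts in 14 days is 14/3 = 4.67 to 14/2 = 7 days, for that period only. The 7-10 day wear time describes the institution's soft cast, which the Background defines with TAO, so longer TAO intervals are equally supported. For Mepitel Ag, 8 days is a ceiling.

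**Putting numbers in.** Assumed: whole-day intervals from a normal distribution with SD 1.5, bounded at 3 and 10 days; for Mepitel Ag, target 8 with anything longer set to 8.

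| Arm, target | m | v | m/2 + v/(2m) | Shift |
|---|---|---|---|---|
| Mepitel Ag, 8, capped at 8 | 7.41 | 0.82 | 3.71 + 0.06 = 3.76 | reference |
| TAO, 6 | 6.01 | 2.24 | 3.00 + 0.19 = 3.19 | +0.57 |
| TAO, 7 | 6.99 | 2.24 | 3.50 + 0.16 = 3.66 | +0.11 |
| TAO, 8.5 | 8.38 | 1.78 | 4.19 + 0.11 = 4.30 | -0.54 |

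Simulated healing with mean 15 and SD 5 days gave about 0.6, 0.1 and -0.6 day. If each burn instead keeps its own interval, the variance term drops out and the shifts are (7.41 - 6.01)/2 = 0.70, (7.41 - 6.99)/2 = 0.21 and (7.41 - 8.38)/2 = -0.48. The size is therefore roughly 0.1-0.7 day, with either sign.

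**An extreme case.** TAO at 4.67 (m = 4.76, v = 1.87, delay 2.38 + 0.20 = 2.58) against uncapped Mepitel Ag at 8 (m = 7.94, v = 2.01, delay 3.97 + 0.13 = 4.10) gives a shift of 4.10 - 2.58 = 1.52 days; simulations gave 1.4-1.7. This stretches the sources twice. The 4.67-day rhythm is carried past day 14, where 62-81% of TAO burns have their recorded healing visit (mean 15, SD 3-7). Also, 37% of Mepitel Ag intervals exceed the 8-day limit. If TAO intervals lengthen to 8 days after day 14 (an assumption), the shift falls to 0.5-0.7 day even with Mepitel Ag uncapped.

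**Effect on the test.** With 50 burns per arm, about 10% marked for surgery and equal 7-day targets, false-positive rates were 4-6% for log-rank and 4-7% for an interval-censored likelihood-ratio test in a log-normal model. Power for a true 2-day benefit at SD 5 was 43-47% and 45-51%. Over a set of scenarios with unequal intervals (mean 15, SD 5, including the extreme case), log-rank ranged over 5-33% false positives and 18-62% power. The interval-censored test stayed at 3-7% and 48-49%.

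**The case against.** The strongest reply is that the harm is conditional and the protocol points away from it. The only trial-specific rule ties the interval to severity, and allocation is balanced on severity. With equal intervals the planned tests behave properly. This stands: a reader might infer that intervals will differ by arm, and the documents do not show that.

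A reader might also infer that the design works against Mepitel Ag by about 1.5 days and would hide most of a 2-day benefit. That reading does not stand either. It treats an 8-day ceiling as a mean, extends a description of the first 2 weeks beyond day 14, and ignores the 7-10 day wear time of the TAO-based cast. With TAO at 8.5 days the sign reverses.

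Nor is half of each arm's own interval (1.5-5 days) a bias. It is a shared delay that cancels when schedules match.

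It can also be said that log-rank makes few assumptions, that a parametric replacement can misfit, and that an interval-censored sensitivity analysis would be enough. The misfit risk is real: a Weibull model on gamma-distributed healing gave 7-10% false positives even with equal intervals. That argues for a semiparametric method. It does not remove the case for using the data as they are observed.

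**Conclusion.** The point holds as a gap in the analysis plan; it is not evidence that the trial is biased. Healing time is interval-censored by design, and Section IV.F does not treat it so. With equal visit spacing there is no bias. With unequal spacing the recorded difference moves by about half the difference in mean interval, in either direction: roughly 0.1-0.7 day in plausible cases, against a planned 2 days. About 1.5 days is an extreme that the documents do not support as an expectation.

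These sizes rest on assumptions that the documents do not supply: mean healing of 15 days with SD 5, an interval SD of 1.5 days, Mepitel Ag changed by day 8, TAO at 6-8.5 days, and the visit date used as the healing date. The half-the-difference rule hardly depends on the healing distribution. The uncertain status of the struck-through sentence changes little, because healing is scored at visits either way. This is an improvement worth considering because it costs little.

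**What to change.** In Section IV.F:

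- Define healing time as lying between the last visit scored below 100% and the first scored 100%, with surgery still right-censored.
- Make the primary comparison a semiparametric proportional hazards or generalized log-rank method for interval-censored data. Choose a form that does not assume equal visit schedules: a label-permutation version does, because arms seen at different times are not exchangeable even when healing is identical. Use a parametric model only if its fit is checked against the nonparametric interval-censored curve.
- Keep Kaplan-Meier and log-rank on visit dates as a sensitivity analysis.
- Report visit intervals by arm.

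This leaves wear time free, so it does not penalize a dressing that can stay on longer.

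The cost is a paragraph of text and a slightly more complex analysis. The healing scores already go into RedCap at each visit, so no extra data, visits or patients are needed. Two limits apply. The figures above for the interval-censored test come from a log-normal model; the semiparametric version was not simulated. The method also assumes that visit timing does not depend on unseen healing, although a check in which nearly healed wounds were seen 2 days sooner still gave 5% false positives.
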